16.4 Study Sample Size, Decision Rule, and Study Duration

16.41 *Sample size:* This study requires 153 evaluable women for the primary endpoint analysis. We anticipate accruing 15 additional patients to account for ineligibility, cancellation, major treatment violation, or other reasons. The maximum projected accrual is therefore 168 women, and we expect a maximum of 60 and a minimum of 40 women within each cohort (photon, proton, and brachytherapy).

16.42 *Study Decision Rule and Operating Characteristics:* Olivotto et al. previously reported interim cosmetic and toxicity results from a randomized trial comparing APBI using 3D-CRT versus WBI. In this study, the same 3DCRT dose and fractionation was used as in the previously discussed NSABP B-39/RTOG 0413 randomized controlled trial comparing 3DCRT or brachytherapy APBI with WBI. At 3 years, the percentage difference in patients with adverse cosmesis in the APBI arm compared to baseline by trained nursing assessment was 10.6%. The proposed analysis is to compute the percentage difference in patients with adverse cosmesis (fair or poor cosmesis) at 3 years compared to baseline. A one-sided 95% confidence interval (with the upper bound of the interval) was computed, by assuming the difference in adverse cosmesis rate at 3 years compared to baseline is 10%, and the distance from 10% to the upper bound of the CI is 4%. The decision rule would be of the following:

- If the upper bound of the one-sided CI for the difference of adverse cosmesis rate lies above 14%, then recommend no further investigation and conclude that there is no sufficient evidence to accept the adverse cosmesis rate of 3 fraction accelerated APBI.
- If the upper bound of the one-sided CI for the difference of adverse cosmesis rate lies below 14%, then recommend further investigation and conclude the increase in 3-year adverse cosmesis rate of 3 fraction accelerated APBI is potentially acceptable.

The study operating characteristics is determined as the chance of declaring that APBI warrants further study, assuming a true value for the difference in adverse cosmesis rate at 3 years compared to baseline for APBI. The table below shows the operating characteristics of this trial with 153 patients and the decision rule given above.

True increase in adverse cosmesis rate at 3 years compared to baseline	Probability of concluding PBI warrants further study
5%	98.4%
10%	72.8%
15%	48.6%
20%	29.8%

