If the increase in APBI adverse cosmesis rate from baseline is 5.0%, there is a 98.4% chance of concluding that the APBI adverse cosmesis increase from baseline is acceptable; this drops to 72.8% if the true rate is 10%, and further drops to 49.6% if the true rate is 15%. If the increase in APBI adverse cosmesis rate from baseline at 3 years is 20% or greater, we are most likely to recommend no further investigations, and conclude that the increase in APBI adverse cosmesis rate is unacceptably high.

Other considerations: Adverse events, quality/duration of response, and patterns of treatment failure observed in this study, as well as scientific discoveries or changes in standard care will be taken into account in any decision to terminate the study.

16.43 Preliminary Analysis: The preliminary analysis is to examine whether the data from the three methods (photon, proton and brachytherapy PBI) can be combined by assessing any difference in the safety profile and baseline patient and tumor characteristics. We will conclude that the variability in the three samples is acceptable and proceed to the primary analysis if all the following conditions are met:

- The difference in rate of grade 3 toxicity between the groups is $\leq 10\%$.
- There is not a significant difference in the rate of IBTR between the groups (using pair-wise chi-squared tests with Bonferroni correction for multiple comparisons).
- The distribution of African Americans and the percentage of cytotoxic chemotherapy use between the groups is not significantly different (using pair-wise chi-squared tests with Bonferroni correction for multiple comparisons).
- The distribution of age between the groups is not significantly different (p -value ≥ 0.05 using a Tukey's test). The difference in age in 10 increments (50-59, 60-69, and ≤ 70) will be reported.
- Tumor size will be dichotomized to two categories ($\leq 1\text{cm}$ vs $1\text{-}2\text{cm}$). The percentage of larger tumor ($1\text{-}2\text{cm}$) between the groups is not significantly different (using pair-wise chi-squared tests with Bonferroni correction).

If any of the above conditions are failed to be met, we will only report the safety and efficacy of each individual arm as secondary and exploratory endpoints.

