16.67 *Distant recurrence incidence*: The distant breast cancer recurrence cumulative incidence will be estimated using a competing risks method (Gooley et al.). The competing risks will be local/regional breast cancer recurrence and death.

16.68 *Disease-free survival*: DFS is defined as the time from registration until the time of disease recurrence or death due to any cause. The DFS will be estimated with a Kaplan-Meier estimator and curve. Estimates will be given for specific time points along with 95% CIs.

16.69 *Overall survival*: The OS will be estimated with a Kaplan-Meier estimator and curve. Estimates will be given for specific time points along with 95% CIs.

16.7 Exploratory Analyses: Exploratory comparisons of the local control, acute and late adverse events, quality of life, and cosmesis among the three radiation regimens will be made. Comparisons of categorical variables will be done with a chi-square test or Fisher's exact test, whichever is appropriate. Comparisons of continuous variables will be done with an ANOVA or Kruskal-Wallis test, whichever is appropriate. Measurements over time (i.e. QOL) will be summarized as area under the curve (AUC) and these values will be analyzed as continuous outcomes. All tests will be two-sided and a p-value less than 0.05 will be considered significant. No adjustments will be made for multiple comparisons.

Correlative Science: Adverse cosmesis has been reported to be significantly increased in prior studies of APBI, yet predictors of adverse cosmesis are poorly understood.^{47,48} If a subset of patients at high risk of complications could be identified, their treatment could be personalized or they could be counseled to pursue other therapeutic options altogether. In the setting of WBI, factors previously reported to be associated with worsened cosmesis include inferior tumor location, large excision volume, the presence of postoperative breast complications, higher dose (including radiotherapy boost), inhomogeneity, and use of concurrent chemotherapy.⁵⁷⁻⁵⁹ In order to begin identifying predictive factors for fair and poor cosmesis following 3 fraction APBI we will analyze clinical and dose volume parameters correlated with increased risk.

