16.10 Inclusion of Women and Minorities

16.11 This study will be available to all eligible patients, regardless of race, or ethnic origin.

16.12 There is no information currently available regarding differential effects of this regimen in subsets defined by race, or ethnicity, and there is no reason to expect such differences to exist. Male breast cancer is a relatively rare entity in whom APBI would not be appropriate therapy and male gender is an exclusion criteria. Although the planned analysis will, as always, look for differences in treatment effect based on racial groupings, the sample size is not increased in order to provide additional power for subset analyses.

16.13 The geographical region served by the Mayo Clinic, has a population which includes approximately 5% minorities. We expect about 5% of patients will be classified as minorities by race and 100% of patients will be women.

17.0 Pathology Considerations/Tissue Biospecimens:

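### Section 16.43 treats non-significance as grounds for calling the three techniques acceptable to pool, yet its IBTR test would usually miss a tripled recurrence rate in one of them

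*Combined protocol and SAP*

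**What the plan says.** Section 16.43 (Preliminary Analysis) sets five conditions. If all are met, the plan states: "We will conclude that the variability in the three samples is acceptable and proceed to the primary analysis".

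- Grade 3 toxicity: the observed difference between groups may not exceed 10%. This is the only numeric limit.
- Recurrence: "There is not a significant difference in the rate of IBTR between the groups", tested "using pair-wise chi-squared tests with Bonferroni correction for multiple comparisons".
- Race and chemotherapy: "The distribution of African Americans and the percentage of cytotoxic chemotherapy use between the groups is not significantly different", with the same tests.
- Age: no significant difference by Tukey's test.
- Tumour size: no significant difference in the share of larger tumours, again by pairwise chi-squared tests with Bonferroni correction.

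If any condition fails, only results by arm are reported, as secondary and exploratory endpoints.

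On group sizes, 16.41 says "This study requires 153 evaluable women for the primary endpoint analysis" and "we expect a maximum of 60 and a minimum of 40 women within each cohort". Section 16.13 says the region served "has a population which includes approximately 5% minorities". The plan gives no power, equivalence margin or assumed 3-year IBTR rate for the check.

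**The concern.** A test that does not reject supports a conclusion of similarity only if it would probably have rejected when a relevant difference existed. Here three small groups are compared on a rare event at a Bonferroni-adjusted level. The smaller the groups, the easier the condition is to meet. The report could then say that variability between techniques had been checked and found acceptable when the check had little chance of finding a clinically relevant difference in recurrence. Real differences are possible: technique is chosen by physician and patient (section 5.0), and the prescription is not the same for every technique (sections 7.11 to 7.13).

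The rule also works in the other direction. Each significance test can reject by chance when the techniques are identical, and one rejection is enough to cancel the pooled primary analysis.

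**Working it through.** **The plan's own figure.** The only sample-size figure is 153, from the precision target in 16.42: n = 1.645² × 0.10 × 0.90 / 0.04² = 152.2, rounded up to 153. It reproduces. It concerns the pooled cosmesis estimate and says nothing about comparisons between techniques.

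**Inputs for the IBTR check.**
- 153 women, split 51/51/51, 40/53/60 or 60/53/40 (16.41).
- Three pairwise chi-squared tests, each at 0.05/3 = 0.0167, so the critical value is 5.73 on 1 degree of freedom. Section 16.43 names no overall level for these tests. The 0.05 is taken from 16.7: "All tests will be two-sided and a p-value less than 0.05 will be considered significant". No continuity correction is mentioned, so the uncorrected test is the main case.
- Baseline 3-year IBTR: assumed at 1%, 2%, 3%, 4% and 6%. The rates cited in 1.2 run from 1% to 6%, mostly at 4 to 5 years, while 16.3 defines IBTR at 3 years. A value at the low end is plausible but is not given.
- Every woman is taken as followed to 3 years.

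**What it takes to reject.** For x and y events in two groups of n, X² = (x/n − y/n)² / [p(1 − p)(2/n)], with p = (x + y)/(2n). At n = 51:
- 0 vs 5 gives 5.26 (not significant); 0 vs 6 gives 6.38 (significant).
- 1 vs 7 gives 4.88 (not significant); 1 vs 8 gives 5.97 (significant).

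The same minimum counts, 6 against 0 and 8 against 1, apply at n = 40 and n = 60. With rates of 2%, 2% and 6% and 51 women each, the whole trial expects 51 × (0.02 + 0.02 + 0.06) = 5.1 events.

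**Probability that no pair is significant when one technique has three times the rate** (exact enumeration of three binomials):

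| Baseline vs tripled | Uncorrected, 51 each | Uncorrected, range over the three splits | Continuity-corrected, 51 each |
|---|---|---|---|
| 1% vs 3% | 99.6% | 98-99.9% | >99.9% |
| 2% vs 6% | 94.7% | 90-97% | 99.4% |
| 3% vs 9% | 84.4% | 81-88% | 96.2% |
| 4% vs 12% | 73.5% | 73-77% | 90.2% |
| 6% vs 18% | 55.6% | 56-57% | 74.1% |

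For larger gaps from a 2% baseline, the uncorrected check misses 10% in one technique 67-76% of the time. It catches 15% about 64-65% of the time and 20% about 86-88% of the time.

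**Scale.** For 80% power to detect a tripling in a single pair at 0.0167, about 502 women per technique are needed at 2% vs 6%, and 240 at 4% vs 12%.

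**Chance failure with identical techniques.** Assumed rates: IBTR 2%, African American 3%, chemotherapy 10%, larger tumours 40%; conditions independent; 51 each. The probability that any pair is significant is 0.0009, 0.0048, 0.0422 and 0.0475 respectively, and 0.05 for age.

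P(at least one fails) = 1 − 0.9991 × 0.9952 × 0.9578 × 0.9525 × 0.95 = 0.138, about 14%. The 40/53/60 split gives 0.140.

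**The case against.** The plan does not claim to prove similarity. It says only that variability is acceptable. Pooling is justified beforehand by equipoise and the precedent of the national trial (1.4, 16.1), and the check can be read as a screen for gross imbalance. That reading stands in part: the screen does catch very large gaps, as the 20% figure shows. But 16.43 still draws a positive conclusion from the result and makes the primary analysis depend on it.

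The miss figures depend on a baseline the documents do not give. This stands, which is why a range is shown. At every baseline from 1% to 6%, a tripling in a trial of 153 passes more often than not.

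A reader might infer three stronger things, and the documents support none of them.
- That passing the check shows nothing. It makes very large recurrence differences unlikely.
- That a missed recurrence difference would bias the pooled 14% decision. That decision concerns cosmesis, and no route from IBTR to the cosmesis estimate is established.
- That a recurrence difference would be hidden. Section 16.65 estimates IBTR cumulative incidence, and 16.3 and 16.7 plan exploratory comparisons of the techniques.

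The figure of 5% in 16.13 covers all minorities. The number of African American women per technique is therefore at most about 51 × 0.05 = 2.6 if enrolment matches, and the 3% used above is an assumption.

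**Conclusion.** The concern holds as a point about inference. Four of the five conditions in 16.43 take non-significance as grounds for calling the techniques acceptable to combine. At 40 to 60 women per technique the IBTR condition cannot exclude a tripled recurrence rate: the miss is 90-97% at an assumed 2% baseline, falling to 56-57% at 6%, with the uncorrected test at 0.05/3 per pair. A continuity correction makes it weaker. Passing is weak evidence of similarity.

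The same conditions would cancel the pooled primary analysis by chance about 14% of the time with identical techniques, given the assumed rates and independence. The pooled cosmesis estimator is not at fault. The rule that decides whether it is used, and the conclusion drawn from that rule, should be changed.

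**What to change.** In 16.43:

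1. Stop using non-significance as the basis for concluding that variability is acceptable.
2. Report pairwise differences in 3-year IBTR with 95% confidence intervals, and say which differences they exclude. For scale, 1/51 vs 1/51 gives about −8.5 to +8.5 points (Newcombe).
3. Report standardised differences between techniques for race, chemotherapy, age and tumour size.
4. Perform the pooled cosmesis analysis as 16.1 already specifies, with cosmesis by technique shown beside it.
5. Keep the 10-point grade 3 toxicity limit as the stated numeric condition, and restrict the last sentence of 16.43 to failure of that condition.
6. Do not describe the techniques as similar in recurrence unless the interval lies within a margin stated in advance.

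The change needs no new data, but it does alter when the pooled analysis is performed, so it should be made before outcomes by technique are reviewed. There are three costs. The report can no longer say that the techniques were checked and found acceptable to combine on recurrence and baseline factors. A significant imbalance would become a reported caveat and would no longer block pooling. The retained toxicity limit can still fail by chance: with identical grade 3 rates and 51 women each, the probability is 1 − 0.967 = 3.3% at an assumed 5% rate and 1 − 0.840 = 16% at an assumed 10% rate.

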16.0 Statistical Considerations and Methodology

- 16.1 Overview: This is a single arm phase II study evaluating the rate of adverse cosmesis (defined as fair or poor cosmesis) at 3 years, compared to baseline, of 3 fraction accelerated APBI. For the analysis of the primary endpoint, patients will be pooled across the three treatment techniques (photon, proton, and brachytherapy) as was done in the the NSABP B-39/RTOG 0413 national multi-institutional randomized control trial comparing APBI with WBI. The three techniques utilized are recognized as standard options for the delivery of APBI, and there is no evidence that any technique is superior to any other with commonly used dose and fractionation regimens.⁴ The primary endpoint is the difference from baseline in the percentage of patients with adverse cosmesis (fair or poor cosmesis) at 3 years. The intent is to determine whether the difference of adverse cosmesis rate is acceptable. Of interest is whether the 3 fraction accelerated APBI results in an unacceptable increase in the adverse cosmesis rate at the end of 3 years, compared to baseline. If it does not, then the 3 fraction accelerated APBI will be recommended for further study. If the change in adverse cosmesis rate is found to be unacceptable, then the recommendation would be to do no further studies of the 3 fraction accelerated APBI. In addition to adverse cosmesis, this study will assess many additional secondary endpoints including IBTR (both invasive and non-invasive IBTRs will be considered), acute and late toxicity profile, quality of life measures, and translational studies.

16.2 **Primary Endpoint:** The primary endpoint is the percentage difference in patients with adverse cosmesis (fair or poor cosmesis) at 3 years compared to baseline. Cosmesis will be assessed by a trained nurse provider using the Harvard Cosmesis Scale.

All patients meeting the eligibility criteria who have signed a consent form, and begun treatment will be considered evaluable for the primary endpoint.

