16.44 Accrual time and Study duration: Since 10/1/2012 patients have been treated with brachytherapy APBI using an 8 or 10 fraction regimen and prospectively followed as part of a clinical registry at the Mayo Clinic in Rochester, MN. Patient interest in the procedure has steadily increased, and in the last 3 months, 13 patients have been treated (median 4.3 patients per month), all of whom would be eligible for this study. A similar to increased level of accrual of brachytherapy patients is anticipated during the course of this study as familiarity with this procedure amongst surgical and radiation oncology providers rises. With the addition of the photon APBI alternative for patients, we anticipate an accrual rate of 5 patients per month for the first year until the opening of

the Mayo proton facility, after which an accrual of 8 patients per month is anticipated. Therefore, the accrual period for this study is expected to be approximately 3 years. We plan to open this study at the Mayo Clinic in Scottsdale and Jacksonville which will further enhance accrual. Final analysis may begin approximately 5 years after the trial begins, i.e. as soon as the last patient registered has been observed for at least 24 months. A maximum of 60 patients and a minimum of 40 patients will be enrolled per treatment arm.

16.5 **Primary Analysis:** The primary analysis will be to estimate the percentage difference in patients with adverse cosmesis (fair or poor cosmesis) at 3 years compared to baseline. All patients meeting the eligibility criteria who have signed a consent form and started treatment will be in the primary analysis. The percentage difference in patients with adverse cosmesis will be estimated using a binomial estimator (number of women who had an adverse cosmesis event at 3 years minus number of women who had an adverse cosmesis event at baseline, and then divided by total number of women in the primary analysis) and a 95% exact binomial confidence interval. As mentioned above, the following decisions will be made based on the 95% CI:

- ***The upper bound of the 95% CI lies below 14%:*** APBI adverse cosmesis is acceptable.
- ***The upper bound of the 95% CI lies above 14%:*** No evidence to show that APBI adverse cosmesis is acceptable.

16.6 **Secondary Analyses**

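### The probabilities in 16.42 ignore the poolability gate in 16.43: its age check alone limits any favourable decision to about 95%, yet 98.4% is stated

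*Combined protocol and SAP*

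**What the plan says.** Section 16.43 is a preliminary analysis of whether the photon, proton and brachytherapy data can be combined. The trial will "proceed to the primary analysis if all the following conditions are met". There are five conditions, and the third holds two tests, so six variables are checked:

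- Grade 3 toxicity: "The difference in rate of grade 3 toxicity between the groups is" at most 10%.
- IBTR: no significant difference (pairwise chi-squared tests, Bonferroni).
- African American share and cytotoxic chemotherapy use: no significant difference (same method).
- Age: p at least 0.05 by Tukey's test.
- Tumor size, up to 1 cm versus 1-2 cm: no significant difference (same chi-squared method).

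The consequence of failure is explicit: "If any of the above conditions are failed to be met, we will only report the safety and efficacy of each individual arm as secondary". Those results would also count as exploratory.

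The neighbouring sections do not carry this condition. Section 16.1 says "For the analysis of the primary endpoint, patients will be pooled across the three treatment techniques" and gives two outcomes only. If the increase is acceptable, the regimen goes forward ("If it does not, then the 3 fraction accelerated APBI will be recommended for further study"); if not, no further study is recommended. Section 16.5 says "All patients meeting the eligibility criteria who have signed a consent form and started treatment will be in the primary analysis" and then states the 14% decision. Section 16.42 defines its operating characteristics as the chance of declaring that APBI warrants further study, and adds: "The table below shows the operating characteristics of this trial with 153 patients and the decision rule given above". The values are 98.4%, 72.8%, 48.6% and 29.8% at true increases of 5%, 10%, 15% and 20%. On group size, 16.41 says "we expect a maximum of 60 and a minimum of 40 women within each cohort".

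**The concern.** The trial is sized for one pooled decision on 153 women. Under 16.43 that decision exists only if every check passes, so the chance of a favourable conclusion is the chance of passing the gate and meeting the 14% rule. The table covers the second part only, and nothing says that it is conditional on the first. Anyone using 16.42 to judge the design would take 98.4% as the chance of a positive recommendation when the regimen performs well, which the plan as written cannot deliver. Nor does the plan say what is concluded about the regimen if the gate fails: neither outcome in 16.1 covers that case.

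Two of the checks are also incompletely specified. The toxicity condition has no time window, while the plan uses several: first month and up to 3 years in 16.3, and 90 days in 16.61 and 16.62. The size condition has no category for tumors over 2 cm and up to 2.5 cm, which 3.13 and 3.41 admit. Whether the primary result is reported could then turn on choices made after the data are seen.

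**Working it through.** **1. Reproducing the plan's own figures, without the gate.** Inputs from 16.42: assumed increase 10%, distance to the upper bound 4 points, one-sided 95%.

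N = 1.645² × 0.10 × 0.90 / 0.04² = 152.2, rounded up to 153. This matches.

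For the table, take X as binomial with n = 153 and probability equal to the true increase, and call the result favourable if the one-sided 95% upper bound is below 14%. The exact (Clopper-Pearson) bound requires X ≤ 14; the Wald bound requires X ≤ 15.

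| True increase | Stated | Exact bound | Wald bound |
|---|---|---|---|
| 5% | 98.4% | 99.0% | 99.6% |
| 10% | 72.8% | 42.8% | 53.6% |
| 15% | 48.6% | 2.3% | 4.0% |
| 20% | 29.8% | 0.02% | 0.05% |

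The first row is close to the 14% rule with no gate. The other three do not follow from it. Paired-difference and independent-proportion versions were also tried and do not give the table. The text below the table has 49.6% where the table has 48.6%.

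**2. Ceiling from the age check.** A favourable decision requires the whole gate to pass, and so requires the age check to pass:

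P(favourable) ≤ P(gate passes) ≤ P(age check passes).

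Tukey's test over three groups at 0.05 has a familywise error of 5%. Simulated with identical age distributions, it passes about 95.0% of the time at 51/51/51 and at 60/53/40 women per group. The ceiling is therefore about 95%, whatever the association between age and cosmesis. The stated 98.4% is 98.4 − 95.0 = 3.4 points above it. If age and cosmesis are independent, 98.4% becomes 0.984 × 0.95 = 93.5%.

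**3. Addition from the toxicity check.** This is the exact probability that the largest and smallest observed grade 3 rates differ by more than 10 points when the true rate is the same in all three groups. The true rates are assumptions; 8.2 expects grade 3 or greater complications in under 10% of patients.

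| True grade 3 rate | 51/51/51 | 60/53/40 | Ceiling, age and toxicity together |
|---|---|---|---|
| 3% | 0.57% | 0.88% | 0.95 × 0.9943 = 94.5% to 0.95 × 0.9912 = 94.2% |
| 5% | 3.35% | 4.86% | 0.95 × 0.9665 = 91.8% to 0.95 × 0.9514 = 90.4% |
| 10% | 16.0% | 21.0% | 0.95 × 0.840 = 79.8% to 0.95 × 0.790 = 75.1% |

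The last column assumes that the two checks are independent. In women, at 51 per group, 5 versus 0 passes (5/51 = 9.8%) and 6 versus 0 cancels the primary analysis (6/51 = 11.8%).

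The IBTR, race, chemotherapy and size checks lower the ceiling further, by amounts that depend on rates the documents do not fix.

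**The case against.** The gate is a disclosed design choice. Section 16.43 states its purpose, conditions and consequence, and it sits between the decision rule and the primary analysis. Technique is chosen rather than randomized, and the prescribed dose differs between brachytherapy and the other two techniques, so checking poolability is reasonable. This stands, and a reader who infers that the gate is an error that must be removed goes further than the documents allow.

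It can also be said that the table names its basis, 153 patients and the 14% rule, and so describes the rule once the pooled analysis is run. That is a possible reading. But the preceding sentence defines the figures as the chance of declaring that APBI warrants further study, and no passage makes them conditional.

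The excess over the ceiling is 3.4 points in a single row, since the other stated values already lie below 95%. That is true. A reader might infer that the gate merely scales those rows down; in fact they do not follow from the 14% rule at all, which is the larger fault in the table.

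Two further readings are tempting. One is that the gate fails by chance in up to about a third of trials. A figure of 34% can be produced, but only by combining 10% grade 3 toxicity, 6% IBTR, 20% chemotherapy, 5% African American patients, uncorrected chi-squared tests and the least strict Bonferroni reading. The other is that real differences in age or tumor size between techniques will sink the analysis. The documents give no size for such differences, and reacting to them is what the gate is for.

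**Conclusion.** The concern holds as a mismatch between 16.42 and 16.43. The stated 98.4% is unattainable under the plan as written, with a ceiling of about 95% from the age check alone. That ceiling needs only the 0.05 level of Tukey's test and identical ages, which is the most favourable case. The full-gate ceiling is lower, but its value rests on assumed rates: with age and toxicity alone it is about 94% at a true 3% grade 3 rate, 90-92% at 5% and 75-80% at 10%.

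The missing cross-references, the absent conclusion on failure, the unclassified tumors and the unstated toxicity window are plain from the text. The point concerns the reporting of operating characteristics and the definition of the gate. It does not show that pooling, or testing whether to pool, is wrong.

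**What to change.** Keep the gate and make these changes:

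1. Recompute the 16.42 probabilities from the 14% rule, naming the interval method, and make table and text agree at 15%.
2. Then either restate them to include the chance of failing the gate, with the assumed rates shown, or label them as conditional on passing and give the pass probability beside them.
3. Refer to 16.43 in 16.1 and 16.5, and say what is concluded about the regimen if the gate fails.
4. Code tumor size as up to 1 cm versus over 1 cm.
5. State the time window of the toxicity check and how many tests the Bonferroni correction covers.

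As an option for the sponsor and not a required correction, the pooled decision could always be reported, with by-technique estimates beside it and the 16.43 comparisons kept as description. The price is that a pooled figure may average over techniques that differ, and estimates from 40-60 women each would show this only imprecisely.

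The cost is plan wording and a short calculation, with no new data. The downside is that the stated probabilities become less favourable.
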